# PARTNERS HUMAN RESEARCH COMMITTEE

## DETAILED PROTOCOL

### I. BACKGROUND AND SIGNIFICANCE

Spinal cord injury (SCI) results in rapid and severe osteoporosis with decreases in bone mass of up to 45% within the first 3 years after injury. Although this osteoporosis is primarily attributed to loss of weight bearing and associated muscle contractions in the paralyzed limbs, there are important reductions in bone blood flow that impact bone metabolism and bone turnover. Bone is a highly vascularized organ with an extensive network of arteries, arterioles, and capillaries that is critical for bone development, maintenance, and repair; [1], [2] without sufficient and well-regulated blood flow, bone cannot maintain its integrity. [3] Thus, reductions in bone perfusion may be a key contributor to bone loss post SCI.

There is extensive arterial remodeling below the lesion that occurs soon after injury, leading to significant structural maladaptations such as decreased femoral artery diameter and increased wall thickness. [4], [5] These changes relate to significant alterations in both vasoconstrictor and vasodilatory response. For example, decreases in flow with leg dependency are greater in those with SCI, indicating enhanced myogenic vasoconstriction. [6], [7] Moreover, increases in leg blood flow with reactive hyperemia are markedly less in those with SCI, indicating impaired myogenic vasodilatory capacity. [7]–[9] Hence, the extensive structural changes post SCI likely result in diminished flow to the leg due to both greater vasoconstriction and lesser vasodilation. This potentially leads to restricted flow to bone in those with SCI. Furthermore, these hypothesized alterations in vasoconstrictor and vasodilatory capacity may also relate to changes in functional blood flow responses in bone. Compressive loading increases bone metabolism requiring greater blood flow. However, if bone perfusion in response to loading is impaired in SCI due to structural changes, strategies to improve bone health based on loading could be largely ineffective. In addition, the structural changes occurring post injury, relate to alterations in nitric-oxide (NO) mediated vasodilation, another potential key mechanism of maintaining appropriate perfusion to bone. While there is almost no research investigating NO vasodilation in bone in humans, a handful of studies suggest that in skeletal muscle, those with SCI have increased NO-mediated vasodilation compared to controls. [10], [11] This implies that there is either increased NO production or similar peripheral NO that are unopposed by sympathetic vasoconstriction. However, given the lack of information on NO mediated vasodilation in the tibial vasculature, it would be prudent to first establish its potential role in healthy individuals prior to exploration in those with SCI. Afterwards, we will investigate the impact of peripheral vascular remodeling on bone perfusion after SCI. Furthermore, we propose to investigate the effect of mechanical loading, on bone perfusion in those with SCI compared to able-bodied individuals.

A critical limitation to the study of bone blood flow in humans has been the lack of noninvasive assessments. The dense nature of bone makes it difficult to investigate perfusion and the techniques used to quantify circulation in other tissues are either difficult or impossible to apply to bone *in vivo*. This study will use a recently developed custom-made near infrared spectroscopy (NIRS) device that can non-invasively assess blood content in bone. [12] While NIRS has been used to assess perfusion in soft tissue, [13], [14] it has not been extensively used to assess perfusion in bone. However, NIRS has been shown to provide reproducible results in controlled

# PARTNERS HUMAN RESEARCH COMMITTEE

## DETAILED PROTOCOL

conditions, [15] and can track dynamic changes in bone perfusion. [16], [17] In our preliminary work, we used NIRS to assess physiological changes in blood content in the tibial cortical bone in humans. Here, we aim to extend our preliminary work by *examining the impact of structural and functional vascular changes on bone perfusion in SCI and determine bone flow response to different loading conditions.*

### II. SPECIFIC AIMS

- 1) Determine if popliteal artery structural changes are reflected in altered myogenic control of tibial bone perfusion post SCI.

*Hypothesis: Compared to able-bodied, those with SCI will demonstrate greater popliteal artery wall thickness and smaller diameter that will relate to both greater myogenic vasoconstriction (in response to leg dependency) and lesser myogenic vasodilation (in response to reactive hyperemia) in tibial bone.*

- 2) Determine if popliteal artery structural changes are reflected in lesser increases in tibial bone perfusion during compressive loading post SCI.

*Hypothesis: Compared to able-bodied, those with SCI will demonstrate greater popliteal artery wall thickness and smaller diameter that will relate to smaller increases in bone perfusion with increasing loading conditions.*

- 3) Determine if nitric-oxide mediated vasodilation is present in the tibial bone vasculature of able-bodied.

*Hypothesis: In able-bodied, the tibial bone vasculature vasodilates in response to a nitric oxide donor.*

All able-bodied volunteers will complete both aim1 and aim2. Only a subset of volunteers with SCI – those with time since injury between 3 and 24 months post injury – will be included for aim 2. The proposed study will investigate the control of bone perfusion in the SCI population as it relates to vascular remodeling and loading conditions.

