### III. SUBJECT SELECTION

#### **Inclusion criteria**

We anticipate we will recruit 29 individuals (males and females) aged 18 to 40 years with injuries, American Spinal Injury Association Impairment Scale (AIS) A and B and C. For aim 2, only individuals with SCI with complete injuries between 3 and 24 months post injury will be included. In addition, we will recruit 29 healthy individuals (males and females) age and gender matched to enroll for this study.

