## PARTNERS HUMAN RESEARCH COMMITTEE

### DETAILED PROTOCOL

hyperemia/leg dependency. Since the two conditions result in distinct and opposite responses, they should be considered separately. For the data from aim 2, for the three passive loading conditions (10%, 30%, 50% body weight without associated muscle contractions), a 2x3 ANOVA will be used to assess changes in perfusion between groups across loading conditions.

The results of this study will provide invaluable insights into bone perfusion in the paralyzed legs of those with SCI. For both aims, we anticipate that individuals with SCI will have less bone perfusion compared to able-bodied due to the extensive vascular maladaptations. Even if the results are not different between those with SCI and able-bodied, this study will have explored a potentially key contributor to SCI-related bone loss, with major implications in treating osteoporosis.

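### First protocol, Aim 2: all controls are kept but only a subset of SCI volunteers, so the age and gender balance sought by matching is not assured, and the 2x3 ANOVA adjusts for neither

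*Combined protocol and SAP*

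**What the plan says.** All references are to the first of the two protocols in the combined document.

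- **Recruitment** (III. Subject Selection, Inclusion criteria). The SCI group is 29 volunteers aged 18 to 40 with AIS A, B or C injuries. For controls: "we will recruit 29 healthy individuals (males and females) age and gender matched to enroll for this study". Neither the reference group for the matching nor the method (by pair or by frequency) is stated; equal counts of 29 suggest the full SCI group.
- **Who enters Aim 2** (II. Specific Aims). "All able-bodied volunteers will complete both aim1 and aim2. Only a subset of volunteers with SCI" are included, namely "those with time since injury between 3 and 24 months post injury". The inclusion criteria add a second restriction that the aims section lacks: "For aim 2, only individuals with SCI with complete injuries between 3 and 24 months post injury will be included". The size of the subset is given nowhere.
- **Analysis** (VI. Statistical Analysis, Statistics). For the three loads, "a 2x3 ANOVA will be used to assess changes in perfusion between groups across loading conditions". No covariate, re-matching or restriction of controls is mentioned.
- **Sex** (VI. Statistical Analysis, Sample Size). The plan expects no difference between the sexes and notes that the SCI population is mostly male. It makes no comparable statement about age.

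**The concern.** Matching sets the balance for 29 against 29. Aim 2 then removes SCI volunteers but no controls, so any control recruited to resemble a removed volunteer stays in the comparison. The removal depends on time since injury. Current age is age at injury plus time since injury, so a link between the selection and age is plausible.

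This differs from ignoring matching that is in place, which mainly costs precision. Here the comparison itself may be unbalanced. If response to loading varies with age within 18 to 40 years, the Aim 2 group effect would combine injury with an age difference. It could mimic the smaller SCI response that the aim predicts, or hide it.

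**Working it through.** The plan gives no figure for this point to reproduce. The check asks how large the imbalance could be.

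**Inputs from the plan:** 29 controls, 29 SCI volunteers, ages 18 to 40, alpha 0.05.

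**Assumptions (not in the documents):** two-sided test; subset size m = 10, 12 or 17; subset mean age differs from that of the remaining SCI volunteers by D = 3, 5 or 8 years; correlation r of age with response 0.2, 0.3 or 0.5; ages uniform over the range, so the age SD is (40 - 18)/√12 = 6.35 years; controls share the mean age of the full SCI group.

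**Step 1, age gap.** The full-group mean is (m/29) × subset mean + (1 - m/29) × mean of the rest. Hence gap = (1 - m/29) × D. For m = 12 and D = 5: (1 - 12/29) × 5 = 0.586 × 5 = 2.93 years. The gap is zero if m = 29 or D = 0.

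**Step 2, bias in response SDs.** Bias = r × gap/6.35. With r = 0.3: 0.3 × 2.93/6.35 = 0.138.

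**Step 3, false-positive rate of the group contrast, unadjusted, with no injury effect.** SE = √(1/m + 1/29) = √(1/12 + 1/29) = 0.343. Noncentrality = 0.138/0.343 = 0.40 on m + 27 = 39 df, which gives 6.8% in place of 5%.

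| m | D (years) | r | Age gap (years) | Bias (SD) | False-positive rate |
|---|---|---|---|---|---|
| 17 | 5 | 0.2 | 2.07 | 0.065 | 5.5% |
| 17 | 5 | 0.3 | 2.07 | 0.098 | 6.1% |
| 12 | 5 | 0.2 | 2.93 | 0.092 | 5.8% |
| 12 | 5 | 0.3 | 2.93 | 0.138 | 6.8% |
| 10 | 5 | 0.3 | 3.28 | 0.155 | 7.0% |
| 10 | 8 | 0.3 | 5.24 | 0.248 | 10.1% |
| 12 | 5 | 0.5 | 2.93 | 0.231 | 10.1% |
| 17 | 8 | 0.5 | 3.31 | 0.261 | 13.3% |
| 10 | 8 | 0.5 | 5.24 | 0.413 | 19.5% |

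Over the whole grid the bias is 0.04-0.41 SD and the rate 5.2-19.5%. Every setting at 10% or above has D = 8 or r = 0.5.

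Step 3 treats the groups as independent. Simulations with truncated-normal ages and exactly matched controls gave smaller departures in the milder settings: 4.3-5.1% for 17 v 29 with a 5-year shift and r = 0.3-0.5. At m = 10, D = 8, r = 0.5 they gave about 10-12%, and about 5% once age was a covariate.

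**Step 4, a real effect.** For 17 v 29, SE = √(1/17 + 1/29) = 0.305, and a true difference of 0.875 SD has about 80% power. A bias of 0.098 SD changes the noncentrality to (0.875 - 0.098)/0.305 = 2.55 or (0.875 + 0.098)/0.305 = 3.19. Against a critical value of 2.015 (44 df), power is about 70% or 88%, depending on direction.

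**Step 5, which ANOVA term is exposed.** With an age slope γ common to all loads, the expected group difference at load j is δ_j + γ × gap. Between loads j and k the term γ × gap cancels, leaving δ_j - δ_k. The group main effect is biased and the group-by-load interaction is not. The interaction would be biased only if the age slope changed with load, by (γ_j - γ_k) × gap.

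**Step 6, sex.** A 20-point difference in male share between the subset and the other SCI volunteers gives a gap of 0.20 × (1 - m/29), or 13, 12 and 8 points for m = 10, 12 and 17. It biases the result only if response differs by sex.

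**The case against.** The strongest reply is that the bias is possible but not shown. The documents give no ages, ages at injury, subset size or age-response relation. A reader might infer that recently injured volunteers must be younger. That does not follow without the age-at-injury distribution, since a recent injury can occur at any age from 18 to 40. No link between completeness of injury and age or sex is given either. This stands, and makes the point conditional.

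A reader might also infer that Aim 2 has no matching at all. The documents do not support that. If matching is by pair, each Aim 2 SCI volunteer's counterpart is measured, because every control completes Aim 2; the open question is which controls are analysed. Keeping all controls for precision is a legitimate choice.

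The calculation uses a single two-group contrast, whereas the plan has a 2x3 ANOVA and the hypothesis concerns rising loads. This also stands: it limits the concern to the group main effect unless the age slope varies with load.

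The sex component is weak because the Sample Size section expects no sex-related difference. That is an assumption of the plan and not a finding, but nothing in the documents points the other way.

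None of this supplies an age or sex term in the Aim 2 model, or a rule on the comparator.

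**Conclusion.** The structural point holds: matching appears to be set for the full 29 against 29, Aim 2 keeps every control but only some SCI volunteers, and the planned ANOVA does not adjust for either matching variable. Balance in the Aim 2 comparison is therefore not assured.

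Whether this causes bias depends on two things the documents do not establish: an age difference between the subset and the other SCI volunteers, and a response that varies with age. If both hold, the group main effect is biased in an unknown direction. If the subset is younger and response rises with age, the bias favours the hypothesis; if response falls with age, it masks it. Moderate assumptions give about 0.1 SD and a false-positive rate of about 5-7%. The rates of 10% and above in the table should not be read as the expected size. The plan should be changed because the remedy is nearly free, not because a large error has been demonstrated.

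**What to change.** In VI. Statistical Analysis, Statistics, state that Aim 2 keeps all able-bodied volunteers and that the group-by-load model includes age as a covariate, and sex as the other matching variable. The cost is two between-subject degrees of freedom (with m = 12, 39 becomes 37). No new data or visits are needed. An age-by-load term matters only if the age slope is thought to change with load.

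State in III. Subject Selection what the controls are matched to and whether by pair or by frequency. If by pair, add a sensitivity analysis restricted to the counterparts of the included SCI volunteers. This loses some precision: with m = 12, and ignoring any gain from a paired analysis, the SE rises from 0.343 to √(2/12) = 0.408 SD, about 19%.

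Give the expected size of the Aim 2 subset, reconcile the complete-injury restriction between the inclusion criteria and the aims section, and tabulate age and sex for the groups actually compared in Aim 2 as well as for 29 against 29.

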### III. SUBJECT SELECTION

#### **Inclusion criteria**

We anticipate we will recruit 29 individuals (males and females) aged 18 to 40 years with injuries, American Spinal Injury Association Impairment Scale (AIS) A and B and C. For aim 2, only individuals with SCI with complete injuries between 3 and 24 months post injury will be included. In addition, we will recruit 29 healthy individuals (males and females) age and gender matched to enroll for this study.

#### **Exclusion criteria (for both able-bodied and SCI groups)**

## PARTNERS HUMAN RESEARCH COMMITTEE

### DETAILED PROTOCOL

Clinical signs or symptoms of heart disease, hypertension, coronary disease, diabetes, other neurological disease, cancer, abnormal resting ECG, pregnant women, underweight and obese individuals (body mass index between 18.5 and 29.9), use of amphetamines (Ritalin, Adderall, Concerta) in the past 48 hours, tibial fracture or tibial stress fracture in the past 2 years.

Healthy individuals should have no recent weight changes  $\geq$  15 pounds, should not be allergic to nitroglycerin patches, capsules, tablets, ointments, or spray, should not use erectile dysfunction drugs, and should not use guanylate cyclase stimulators, such as riociguat. Concomitant use can cause hypotension.

Healthy individuals should not use PDE-5 inhibitors, such as avanafil, sildenafil, tadalafil, vardenafil hydrochloride. Concomitant use can cause severe hypotension, syncope, or myocardial ischemia.

Healthy individuals should not have severe anemia. Nitroglycerin is contraindicated in patients with severe anemia (large doses of nitroglycerin may cause oxidation of hemoglobin to methemoglobin and could exacerbate anemia).

Those with SCI will have no extreme spasticity to avoid spontaneous contractions and cannot be on baclofen due to its potential autonomic effects.

#### **IV. SUBJECT ENROLLMENT**

We will recruit from eligible ASRT participants study (Partners IRB Protocol # 2013P000604. Additionally, we will rely on word of mouth and referrals from the spinal cord injury program, the outpatient therapy department, and the Exercise for Persons with Disabilities (ExPD) program at Spaulding Rehabilitation Network to enroll participants in this study. Flyers will be posted at SRH outpatient sites and/or given to potential subjects along with a phone number to call if they are interested in learning more about the study. Our laboratory has been regularly enrolling SCI patients for research from the SRN. For the able-bodied participants, in the past, we have successfully recruited young males and females by posting flyers on college campuses and/or by posting on internet websites. The website ad has a short description of the project and a number to contact if they would like more information. When the potential subject makes contact with the study staff, we use a phone screening of health questions and a short description of the study. This process usually takes 15 to 20 minutes. If individuals meet eligibility requirements from the phone screening and are interested in participating, they are then scheduled for a physical screening. At that time, we mail a consent form to give opportunity to read and understand the specifics of the study.

Research study staff will obtain volunteer consent in accordance with guidelines established by the Institutional Review Board during the study visit to the Cardiovascular Laboratory. Participants are encouraged to ask questions and are reminded that participation is strictly voluntary and will not affect their current or future care at Spaulding Rehabilitation Hospital or any of its affiliates.

#### **V. STUDY PROCEDURES**

##### **Study Visit**

# PARTNERS HUMAN RESEARCH COMMITTEE

## DETAILED PROTOCOL

Once recruited for the study, the volunteers will visit the laboratory for a health screening session to further determine eligibility. This 30-minute screening session includes obtaining informed consent, health history, and obtaining weight and tibial length measurements.

Once volunteers complete the screening process and meet the study inclusion criteria they will continue the visit to investigate tibial perfusion in response to leg dependency, reactive hyperemia, and increasing loading conditions. The study visit will take approximately 3 hours for participants that complete both aims and approximately 1.5 hours for those with SCI that complete only aim 1.

### **Detailed procedures**

At the beginning of the study visit, we will obtain measurements of the popliteal artery thickness and lumen diameter using Doppler ultrasound (SonoSite Edge II, Fujifilm SonoSite). Throughout the study for the first aim, we will measure whole leg blood velocity in the popliteal artery using Doppler ultrasound (Multidop T2, DWL). Throughout the protocol, volunteers will be instrumented for measurement of tibial blood flow using a NIRS system (see Measurements below). The measurements will be taken in the same leg.

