# PARTNERS HUMAN RESEARCH COMMITTEE

## DETAILED PROTOCOL

*Beat-by-Beat Calf Blood Flow.* We will use Doppler derived flow velocities to estimate whole limb blood flow through the popliteal artery. A continuous wave 4 MHZ Doppler probe (Multidop T2, DWL) is placed against the skin under the knee to isolate the popliteal artery proximal to the bifurcation.

*Popliteal Artery Structure.* A linear 6- to 15- MHz Doppler ultrasound (SonoSite Edge II, Fujifilm SonoSite, Bothell, WA) will be used to measure popliteal artery thickness and lumen diameter. The measurements will be taken at the distal popliteal artery above 2cm above arterial take-off, with the subject in supine position with the knee flexed at 45deg. The arterial diameter will be measured on transverse images, with the ultrasound beam perpendicular to the artery. [18]

*Tibial Length.* Tibial length will be measured in sitting position with a tape measure.

*Body Weight.* Weight will be measured on a scale.

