#### Statistics

Data from NIRS monitoring will be used to determine hemoglobin content changes in tibial bone from changes in light absorption on a moment-by-moment basis. A detailed description of the analysis can be found in our previous work. [12] Briefly, NIRS monitoring provides a change in hemoglobin content from one state to another. This is due to the fact that absolute intensity of the scattered light measured across the tibia cannot be used for an absolute measure of perfusion. However, as perfusion increases, there is a proportional increase in absorption (and vice versa). Thus, percent change in total hemoglobin detected reflects the relative change in perfusion.

The main outcomes assessed will be popliteal artery thickness and lumen diameter, tibial perfusion, and whole leg blood flow. This project will employ a simple and straightforward statistical approach to compare responses within and between groups. Statistical significance will be set at 0.05, and power at 80%. Descriptive statistics will be presented including mean, median, standard deviation, and range. Differences/relations will be considered as statistically significant at alpha=0.05 level. For all parametric statistical tests, conformity of data to required statistical assumptions will be verified using standard methods. If assumptions for parametric tests do not hold, non-parametric alternatives will be employed. The analysis plan is written as though there are no distributional problems; assumptions for all analyses will be checked and analogous methods calling for fewer and/or weaker assumptions will be used, if called for. For the data from aim 1, unpaired t-tests will be used to assess changes in perfusion between groups and reactive

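### The plan does not provide for masked reading of popliteal wall thickness and lumen diameter, two main outcomes with a stated expected direction

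*Combined protocol and SAP*

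**What the plan says.** The combined document holds two protocols. This point concerns the one on vascular structure and loading.

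- **Timing.** Detailed procedures, for the start of the visit: "we will obtain measurements of the popliteal artery thickness and lumen diameter using Doppler ultrasound".
- **What comes before.** V. Study Procedures, Study Visit: "This 30-minute screening session includes obtaining informed consent, health history, and obtaining weight and tibial length measurements". Those who qualify then go on with the visit.
- **Method.** Measurements, Popliteal Artery Structure, names a linear 6- to 15-MHz ultrasound device that "will be used to measure popliteal artery thickness and lumen diameter". For the lumen it adds: "The arterial diameter will be measured on transverse images, with the ultrasound beam perpendicular to the artery". No imaging plane is given for wall thickness.
- **Status.** VI. Statistical Analysis, Statistics: "The main outcomes assessed will be popliteal artery thickness and lumen diameter, tibial perfusion, and whole leg blood flow".
- **Expected direction.** II. Specific Aims, Aim 1: "Compared to able-bodied, those with SCI will demonstrate greater popliteal artery wall thickness and smaller diameter". The Aim 2 hypothesis repeats it.

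The protocol does not say who scans, who reads, whether the reader knows the group, how many readings are taken, or whether repeatability is checked. Monitoring and Quality Assurance covers completeness, consent and adherence. Neither protocol mentions blinding or masking of any kind.

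**The concern.** Group cannot realistically be hidden from whoever scans the leg. Paralysis is visible, health history is taken beforehand, and participants with SCI are recruited largely through SCI and therapy programmes. The expected result is written into the aims, and the Background describes arterial remodelling after SCI as established. If the person who measures the image also knows the group, small choices in placing the measurement points can lean toward a thicker wall and a smaller lumen in SCI.

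Two results would be exposed. One is the direct comparison of structure between groups. The other is any relation between structure and perfusion estimated with the groups pooled, since structure is the explanatory variable in Aims 1 and 2. A larger sample would not cure this: a systematic shift stays while the standard error shrinks.

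**Working it through.** **No plan figure to reproduce.** The plan gives no SD, reader error or repeatability for thickness or diameter, and names no test for either. The calculation below is a hypothetical sensitivity range.

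**Inputs**

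- Group size n = 29 with SCI and 29 able-bodied (VI, Sample Size), taken as stated. The same section describes a base of 17 plus 17 more per group, which is 34. That mismatch is a separate matter and the argument here does not depend on it.
- Significance level 0.05 (VI, Statistics). The plan does not state sidedness; two-sided is assumed.
- Test: unpaired t-test. This is an assumption, because the plan names that test only for Aim 1 perfusion.
- True difference in structure: zero (assumed).
- Systematic reading shift b between groups, in units of the within-group SD: 0.1, 0.2, 0.3 and 0.5 (assumed).

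**Step 1: error rate under a reading shift**

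Degrees of freedom = 2 × 29 − 2 = 56. Critical value t(0.975, 56) = 2.003. Noncentrality = b × √(n/2) = b × √14.5 = 3.808b. The rejection rate is the probability that a noncentral t exceeds 2.003 in absolute value.

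| Shift b (SD) | Noncentrality | Two-sided rejection | Of which in the hypothesised direction |
|---|---|---|---|
| 0 | 0 | 5.0% | 2.5% |
| 0.1 | 0.381 | 6.6% | 5.6% |
| 0.2 | 0.762 | 11.6% | 11.3% |
| 0.3 | 1.142 | 20.2% | 20.1% |
| 0.5 | 1.904 | 46.5% | 46.5% |

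Hand check by the normal approximation at b = 0.5: Φ(1.904 − 1.960) = Φ(−0.056) ≈ 47.8%, close to the exact 46.5%.

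**Step 2: if structure truly differs**

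The problem is then exaggeration rather than a false positive. With 29 per group, the difference detectable with 80% power is 0.75 SD. If the true difference were 0.75 SD, a shift of 0.1 SD would inflate the estimate by 0.1/0.75 = 13%, and a shift of 0.5 SD by 0.5/0.75 = 67%.

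**Step 3: which analyses a shift can reach**

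- *Aim 1 named test:* unpaired t-tests of perfusion change. Structure does not enter, so there is no effect.
- *Aim 2 named test:* a 2×3 ANOVA of perfusion across loads. Structure does not enter, so there is no effect.
- *Group comparison of structure:* affected as in Steps 1 and 2.
- *Structure-perfusion relation within a group:* a constant shift moves every reading in that group equally, so the slope is unchanged.
- *Structure-perfusion relation pooled over groups:* with x for structure and y for perfusion change, the pooled cross-product is the within-group part plus (n/2)·Δx·Δy = 14.5·Δx·Δy, where Δ is the group difference in means. A reading shift b, expressed in the units of x, adds 14.5·b·Δy. This favours the hypothesis if perfusion also differs in the anticipated direction, and adds nothing if Δy = 0.

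The figure of 29 fits the Aim 1 comparison. Aim 2 takes only a subset of the SCI group, whose size the plan does not give.

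**The case against.** The strongest reply is that unmasked reading is inferred from silence. Detailed procedures says when the measurements are obtained, but not that they are read live or by someone who knows the group. Measuring the diameter on images is equally compatible with storing them and reading them later, possibly coded. That stands. A reader might infer that the procedure as written yields unblinded readings; the documents support only that masked reading is not provided for.

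A reader might also infer that both aims collapse if structure is misread. They do not: the named tests for Aims 1 and 2 contain no structural variable (Step 3). The plan names no test of structure at all, which is a gap of its own.

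The percentages are open to challenge too. Nothing in the documents anchors shifts of 0.1 to 0.5 SD, and 47% belongs only to the largest. They assume no true difference, whereas the Background cites narrower femoral arteries and thicker walls after SCI. They also ignore the matching on age and gender. All of this stands, so the figures show sensitivity and do not predict.

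Finally, coding the images does not mask the scan. Probe position, angle and choice of image stay with an operator who sees the participant, and the description of the measurement site is unclear. This limits the remedy but does not remove its value for the reading step.

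**Conclusion.** The point holds as a gap in protection against reading bias. Two main outcomes with a directional hypothesis are obtained when the group is evident, and nothing in either protocol provides for masked reading. Any expectation bias would act in the hypothesised direction in a group comparison of structure. It could do so in a pooled structure-perfusion relation if perfusion also differs as anticipated.

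Its size is unknown. Under the stated assumptions, a shift of 0.1 to 0.5 SD would take a nominal 5% error rate to about 7% to 47%. The documents do not show that any bias occurs or that the named perfusion tests are affected. A reader might extend the point to the choice of near-infrared and Doppler analysis windows, but it rests on image reading and does not carry over. The protocol fixes the baseline, stimulus and recovery durations, so window choice would need its own argument.

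The change is worth making because it is cheap and protects two main outcomes. Confidence is medium, because how the images will be read is not stated.

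**What to change.** Amend Detailed procedures and the Popliteal Artery Structure paragraph under Measurements so that:

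1. images are captured and stored at the visit under a study code with no group label;
2. existing staff, preferably someone who did not scan that participant, measure wall and lumen offline, in an order shuffled across both groups and by a fixed written rule;
3. the measurement file is locked before the group key is merged.

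If reading is already done this way, the amendment need only say so.

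The cost is a small coding step and a delay between visit and reading, with no added participants, equipment or visit procedures. Having a reader who did not scan the participant depends on staffing, which the documents do not describe. The change removes reading bias only, not bias in probe placement or image selection at capture.
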